## **8. TRIAL PROCEDURES**

Methodology training for investigators: At the start of the study, the principal investigators will undergo methodology training and practice the use of the hand held SentiMag probe device. The chief investigator will standardize the sentinel lymph node biopsy technique during this feasibility study.

Screening and preliminary discussion of research project with potential participant: During the standard pre-operative clinic visit patients who have been identified as potential participants will be screened and informed about the study by a clinician or colorectal specialist nurse. They will have an opportunity to ask questions and will be provided with an information sheet.

Informed consent: In the endoscopy unit a clinician will discuss the study further and take consent if the patient is willing to proceed. A letter will be sent to the participant's GP informing them of the study.

Endoscopic injection of tracer and post-injection monitoring: The magnetic tracer will be injected approximately 5 days before surgery during endoscopic assessment of the tumour. The rectal tumour

will be visualized by endoscopy, as per standard clinical practice. Up to 2ml tracer solution will be infiltrated systematically (in 4 quadrants) into the submucosa around the rectal tumour. After the procedure, patients will be monitored for 1 hour to ensure no hypersensitivity or adverse reactions occur and provided with a contact telephone number in case of any delayed reaction or side-effects on discharge.

MRI scan of pelvis: On the same day as the endoscopy unit visit or the day of surgery, patients will undergo an MRI scan of the pelvis. This will be done 2-3 hours after the endoscopic injection of tracer or on the day of surgery.

Rectal cancer surgery: Patients will undergo rectal cancer surgery according to their clinical indication. During surgery for the “ex-vivo” group, indocyanine green dye (ICG) will be injected near the tumour. At the conclusion of surgery the surgeon will make an assessment as to whether the tracer injection affected surgery, for example by causing inflammation in the tissue planes.

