## **8.6. Subsequent Visits**

[Visit 1: clinic] Potential participants will be informed about the study by the study investigators or the colorectal nurse specialists at their initial hospital clinic visit with the operating surgeon. This is part of the clinical work-up of a patient and therefore would not involve an additional visit for the participant. This visit will take place approximately 2-3 weeks prior to surgery. Information will only be given to patients who are already aware of their diagnosis. Patient information sheets will be given to the patient at this stage. Patients will be screened using the inclusion and exclusion checklist.

[Visit 2: endoscopy suite] Surgeons assess rectal cancers by endoscopic means in order to plan surgery. This is part of normal practice and will not involve an additional visit for the potential participant. This usually occurs a week before surgery. Informed consent will be obtained from participants at this stage. During the endoscopic procedure the tracer will be injected around the rectal tumour. Patients will be monitored for 1 hour following this for any adverse effect of the injection.

[Visit 3: Radiology suite] Patients will have an MRI scan to assess tracer uptake into the mesorectum. This is not part of the standard routine care and will involve an additional hospital visit for the patient. This will be undertaken 2-3 hours after the endoscopic injection, on the same day as the endoscopy visit or prior to surgery on the day of surgery.

[Visit 4: Admission to hospital for surgery]: This is part of normal practice and will not involve an additional visit for the potential participant. Sentinel node sampling will take place after surgery from the resected specimen (“ex-vivo” phase) or during surgery (“in-vivo” phase). Participants will be monitored during their post-operative stay in hospital as part of normal practice. The incidence of post-operative complications will be recorded on discharge.

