## **9. IDENTIFICATION & DESCRIPTION OF THE INVESTIGATIONAL DEVICE**

### **9.1. Device description**

This study will use Sienna+® or Magtrace® tracer which contains magnetised nanoparticles and a hand-held SentiMag® probe within its CE market intended purpose for sentinel lymph node mapping. Lymph node mapping is used in cancer patients to identify the first lymph nodes that would be affected by spread of the cancer. Specifically, in this study, the device will be used to identify sentinel lymph nodes in the mesorectum of patients with rectal cancer.

The tracer is a dark brown aqueous suspension of organically coated superparamagnetic iron oxide particles, supplied in a vial. It will be diluted and injected during endoscopy. The vials will be supplied directly and will not involve pharmacy.

The manufacturer is Endomagnetics Limited, [name]. The Sienna+ product has been in use since 29 February 2012. On 31 October 2018 Endomagnetics discontinued Sienna+ and replaced it directly with Magtrace, which contains the same nanoparticle, in the same amount and concentration, but formulated in 0.3% saline rather than water.

At the start of the study, the principal investigators will undergo methodology training and practice the use of the hand held SentiMag probe.

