## **12. STATISTICS**

### **12.1. Description of Statistical Methods**

All data will be stored in an Excel worksheet and analysed using Excel and R.

Frequency of event (adverse, hypersensitivity or complication) will equate to: number of adverse event/total number of recruited patients.

Frequency of tracer detection at surgery (at tumour site and in lymph nodes) will equate to: number of operations where tracer seen/ total number of operations on recruited patients.

Impact of tracer injection on subsequent surgery will be assessed by the surgeon's binary assessment as to whether surgery was more difficult than expected, and also free text comments to be analysed qualitatively.

A sentinel lymph node will be defined as the first lymph node draining the tumour and positivity defined according to the manufacturer's instructions. A "positive" node will be defined as having over 10% of the tracer activity of the site of initial submucosal injection. A "negative" node will be defined as having less than 10% of the tracer activity of the site of initial submucosal injection.

The detection rate for sentinel lymph nodes on MRI scan and Sentimag probe assessment will equate to: number of patients/specimens in whom a sentinel lymph node is identified/total number of examined patients/specimens.

MRI and Sentimag mapping will be qualitatively compared for all relevant patients/specimens (as appropriate) to establish a baseline of individual variability.

The presence and location of lymph nodes in the mesorectal specimen will be compared with the pathology findings for each patient in the ex-vivo part using correlation.

The success rate for removing the sentinel lymph node during TEM surgery will equate to: number of patients in whom the sentinel lymph node was removed/total number of patients undergoing TEM operation.

As this is a feasibility study, results will be continuously evaluated and adjustments made to the tracer dosage and timing of injection if indicated.

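### Tracer dosage and injection timing may be adjusted on accumulating results, yet the main feasibility rates are defined only as pooled ratios with no breakdown by regimen

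*Combined protocol and SAP*

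**What the plan says.** Section 12.1 of the combined protocol and SAP provides that "results will be continuously evaluated and adjustments made to the tracer dosage and timing of injection if indicated". It gives no trigger, decision-maker or log, and no point at which the regimen counts as settled.

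The same section defines the rates:

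- Primary A: "number of adverse event/total number of recruited patients".
- Primary B: "number of operations where tracer seen/ total number of operations on recruited patients".
- Sentinel-node detection (MRI and probe): patients or specimens with a sentinel node identified, divided by all those examined.
- TEM success: patients with the node removed, divided by all patients having TEM, so in-vivo patients only.
- Primary C has no written ratio. It rests on the "surgeon's binary assessment as to whether surgery was more difficult than expected, and also free text comments to be analysed qualitatively".

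Section 12.6 analyses everyone injected and adds no breakdown by regimen. Section 12.7 treats reporting of deviations from the statistical plan as not applicable.

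On the regimen itself, section 8 gives the volume as an upper limit of 2 ml and says: "The magnetic tracer will be injected approximately 5 days before surgery during endoscopic assessment of the tumour". Section 8.6 says of the endoscopy visit, at which the tracer is injected: "This usually occurs a week before surgery". Section 9.1 says the tracer is diluted, without giving the dilution, and describes Magtrace as a direct replacement for Sienna+, "formulated in 0.3% saline rather than water". Appendix C records a changed dosage specification (version 1.2) and the product replacement (version 1.3). Section 9.2 has injection details recorded on the CRF.

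**The concern.** Primary B asks whether tracer is still present and detectable when the patient reaches surgery. The amount injected and the time between injection and surgery bear directly on that, and they are the two things section 12.1 lets the team change. Because changes respond to results, a pooled rate could mix patients treated under a regimen that was dropped with patients treated under the one that was kept. The weights would depend only on when the change happened.

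Section 4 says a clinical trial of sentinel-node biopsy is intended next. Its planners need the detection rate, and the adverse-event rate, under the procedure they would actually use. A low pooled rate could hide a final regimen that works. A satisfactory pooled rate could hide a later change that did not help. Following section 12.1 as written would not produce the figures needed to tell these apart.

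**Working it through.** **Inputs from the documents.** 20 ex-vivo patients and 20 in-vivo patients (section 12.2); total 40 (synopsis). 20 + 20 = 40 agrees. The plan states no target rate, precision, significance level or power, so it has no other figure to reproduce. All detection rates below are assumptions chosen to show a range.

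**Step 1: what pooling does.** With n1 patients at rate p1 before a change and n2 at rate p2 after it:

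pooled rate = (n1·p1 + n2·p2) / (n1 + n2)

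pooled rate − final rate = −[n1/(n1 + n2)]·(p2 − p1)

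Exact (Clopper–Pearson) 95% limits for x/n are the 2.5% quantile of Beta(x, n−x+1) and the 97.5% quantile of Beta(x+1, n−x).

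| Before | After | Pooled (95% CI) | Final regimen (95% CI) | Pooled − final |
|---|---|---|---|---|
| 5/10 | 9/10 | 14/20 = 70% (45.7–88.1) | 90% (55.5–99.7) | −0.5 × 40 = −20 points |
| 6/10 | 9/10 | 15/20 = 75% (50.9–91.3) | 90% (55.5–99.7) | −0.5 × 30 = −15 points |
| 7/10 | 9/10 | 16/20 = 80% (56.3–94.3) | 90% (55.5–99.7) | −0.5 × 20 = −10 points |
| 12/20 | 18/20 | 30/40 = 75% (58.8–87.3) | 90% (68.3–98.8) | −0.5 × 30 = −15 points |
| 5/10 | 27/30 | 32/40 = 80% (64.4–90.9) | 90% (73.5–97.9) | −0.25 × 40 = −10 points |

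In the first and fourth rows the upper limit of the pooled interval lies below the final regimen's 90%. If p1 = p2, or if no change is made, the last column is zero.

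**Step 2: could the trial show that pooling is harmless?** Approximate power to detect 60% against 90% at two-sided 5% is 33% with 10 v 10 and 60% with 20 v 20. A non-significant difference between regimens would therefore not justify pooling them.

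**Step 3: what splitting costs.** At an assumed 80% detection rate:

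| Patients carrying the rate | Detected | 95% CI | Upper 95% limit if no adverse reaction is seen, 1 − 0.025^(1/n) |
|---|---|---|---|
| 40 | 32 | 64–91% | 8.8% |
| 20 | 16 | 56–94% | 16.8% |
| 10 | 8 | 44–98% | 30.8% |
| 5 | 4 | 28–99.5% | 52.2% |

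The intervals widen quickly, so the split should follow formally adopted regimens only.

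**The case against.** Adapting dosage and timing is a proper purpose of a feasibility study, and the plan declares it openly. Section 12.3 sets no significance level, so no error rate is being compromised. Adjustments happen only if indicated, and the documents do not say how many patients, if any, were treated under each version of the dosage specification. All of this stands. The gap is in reporting, not in the decision to adapt.

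Two further objections limit the remedy.

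- Patients treated after the last results-driven change are selected by outcome. If every failure prompted a change, the final run would hold only successes, or no patients, even if the changes did nothing. The final-regimen rate can therefore flatter.
- Volume (an upper limit) and interval (approximate) can vary between patients with no adjustment at all. Splitting on actual values could break 40 patients into many small cells.

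A reader might also infer more than the documents support:

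- *That every endpoint is one ratio over all patients.* TEM success covers TEM patients only, the pathology comparison is an ex-vivo correlation, MRI and probe mapping are compared qualitatively, and primary C has no written ratio.
- *That the product switch made a different procedure.* Section 9.1 says the particle, its quantity and its concentration are unchanged and only the carrier differs. Nothing suggests worse performance. This justifies a descriptive table by product and no more.
- *That section 12.1 conflicts with section 16.4 on approval of amendments.* Section 12.1 does not say that adjustments bypass approval, and Appendix C shows a dosage change made by amendment.
- *That technique was altered from results.* The sentence "The chief investigator will standardize the sentinel lymph node biopsy technique during this feasibility study" describes reducing variation, not a change of setting.

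**Conclusion.** The point holds conditionally. Section 12.1 permits results-driven changes to dosage and timing, and provides only pooled ratios for primary A, primary B and the sentinel-node detection rate. TEM success pools any change within its own phase. Once a change is adopted, those figures describe a mixture and not the procedure to be taken forward. In the illustrations the pooled rate falls 10 to 20 percentage points below the final regimen's rate. That range rests on assumed rates and assumed timing of the change, and is zero without a change.

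The documents do not support saying that the reported rates necessarily describe no single procedure, since that depends on whether patients were in fact treated under different regimens. The two statements of the injection interval are both approximate. They need reconciling but are weak evidence of a changing regimen. This is worth correcting before analysis. It does not invalidate the study.

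**What to change.** Amend section 12.1 as follows.

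1. Log each formally adopted change in dosage or timing, with its date and reason.
2. Record for every patient the product, volume, dilution and actual injection-to-surgery interval.
3. Report primary A, B and C, the sentinel-node detection rate and TEM success by phase and by formally adopted regimen, in enrolment order, with exact 95% intervals, beside the pooled figure. Do not split on incidental patient-level variation. For primary A, an exact binomial interval needs patients with at least one event as the numerator.
4. Tabulate results by product descriptively.
5. Present the final-regimen rate as the one relevant to the next trial, state that it follows results-driven changes, and keep all earlier patients in the report.
6. Reconcile the injection interval in section 8 with that in section 8.6.

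No dose, interval or rule on when adjustments may be made is proposed.

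The cost is SAP wording and one extra table. Section 9.2 already has injection details recorded, but it does not name volume or dilution, so the CRF may need those fields. The statistical cost is smaller denominators and wider intervals per regimen. If no change was adopted, the regimen breakdown reduces to a split by phase.

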#### **12.2. The Number of Participants**

The first (ex-vivo) part of the study will recruit 20 patients due to have radical surgery for rectal cancer in order to establish the accuracy of sentinel node detection using Sienna+ tracer by ex-vivo specimen analysis. This number is based on previously published sentinel node studies in breast cancer and melanoma (O'Hea et al, 1992; Brouwer et al, 2012). The second (in-vivo) part will recruit a further 20 patients, but these will be people with early rectal cancer scheduled for a less invasive TEM operation to treat their rectal cancer.

#### **12.3. The Level of Statistical Significance**

Not applicable for this proof of concept study

#### **12.4. Criteria for the Termination of the Trial**

Any serious adverse event will prompt a review of the study and possible termination.

#### **12.5. Procedure for Accounting for Missing, Unused, and Spurious Data.**

All available data will be used. Missing data will not be imputed. Spurious data will be re-checked, and if valid will be included in the analysis.

#### **12.6. Inclusion in Analysis**

All patients who receive the tracer injection will be included in the analysis.

### **12.7. Procedures for Reporting any Deviation(s) from the Original Statistical Plan**

Not applicable. The analysis involves only simple statistical measures, and all proposed measures are necessary to determine feasibility.

## **13. DATA MANAGEMENT**

### **13.1. Source Data**

Source documents are where data are first recorded, and from which participants' CRF data are obtained. These include, but are not limited to, hospital records (from which medical history and previous and concurrent medication may be summarised into the CRF), clinical and office charts, laboratory and pharmacy records, diaries, microfiches, radiographs, and correspondence.

CRF entries will be considered source data if the CRF is the site of the original recording (e.g. there is no other written or electronic record of data). All documents will be stored safely in confidential conditions. On all trial-specific documents, other than the signed consent, the participant will be referred to by the trial participant number/code, not by name.

### **13.2. Access to Data**

Direct access will be granted to authorised representatives from the Sponsor, host institution and the regulatory authorities to permit trial-related monitoring, audits and inspections. Data will not be transferred outside of the UK.

### **13.3. Data Recording and Record Keeping**

Data will be recorded using paper CRFs and entered into an Excel spreadsheet. Data from this study will be generated and analysed at the Oxford University Hospitals by the research investigators. Personal data will be stored and accessed by the investigators for less than 3 months. Research data will be stored for 10 years after the completion of the study.

The participants will be identified by a unique trial specific number and/or code in any database. The name and any other identifying detail will NOT be included in any trial data electronic file.

All electronic data will be password-protected and anonymised. All hard copy files and data will be kept in a locked cabinet within a locked office with restricted access. Access to the data will be restricted to study team members. The NHS Code of Confidentiality will be followed. This study will follow the sponsor organisation's policy regarding data storage and the NHS Code of Confidentiality. Information derived from the study will be stored on a single, secure (password encryption) NHS computer. This will be positioned within a secure location in the hospital.

All participants will be informed using patient information sheets of how data will be stored. The principal investigators will constantly review the security of research data files.

#### **14. QUALITY ASSURANCE PROCEDURES**

The trial will be conducted in accordance with the current approved protocol, ICH GCP, relevant regulations and standard operating procedures.

Regular monitoring will be performed according to ICH GCP. Data will be evaluated for compliance with the protocol and accuracy in relation to source documents. Following written standard operating procedures, the monitors will verify that the clinical trial is conducted and data are generated, documented and reported in compliance with the protocol, GCP and the applicable regulatory requirements.

#### **15. SERIOUS BREACHES**

A serious breach is defined as “A breach of GCP or the trial protocol which is likely to affect to a significant degree –

- (a) the safety or physical or mental integrity of the subjects of the trial; or
- (b) the scientific value of the trial”.

In the event that a serious breach is suspected the Sponsor must be contacted within 1 working day. In collaboration with the C.I., the serious breach will be reviewed by the Sponsor and, if appropriate, the Sponsor will report it to the REC committee, Regulatory authority and the NHS host organisation within seven calendar days.

#### **16. ETHICAL AND REGULATORY CONSIDERATIONS**

##### **16.1. Declaration of Helsinki**

The Investigator will ensure that this trial is conducted in accordance with the principles of the Declaration of Helsinki. These details are provided in the protocol.

##### **16.2. ICH Guidelines for Good Clinical Practice**

The Investigator will ensure that this trial is conducted in full conformity with relevant regulations and with the ICH Guidelines for Good Clinical Practice (CPMP/ICH/135/95) July 1996.

##### **16.3. Medical Device regulations**

The Investigator will ensure that this trial is conducted in full conformity with:

- European Commission Medical Device Guidelines relating to the application of the EU Directives on Medical Devices
- Guide to European Medical Device Trials and BS EN ISO 14155

#### **16.4. Approvals**

The protocol, informed consent form, participant information sheet and any proposed advertising material will be submitted to an appropriate Research Ethics Committee (REC), regulatory authorities (MHRA in the UK), and host institution(s) for written approval.

The Investigator will submit and, where necessary, obtain approval from the above parties for all substantial amendments to the original approved documents.

#### **16.5. Reporting**

The CI shall submit once a year throughout the clinical trial, or on request, an Annual Progress Report to the REC, host organisation and Sponsor. In addition, an End of Trial notification and final report will be submitted to the MHRA, the REC, host organisation and Sponsor.

#### **16.6. Participant Confidentiality**

The trial staff will ensure that the participants' anonymity is maintained. The participants will be identified only by initials and a participants ID number on the CRF and any electronic database. All documents will be stored securely and only accessible by trial staff and authorised personnel. The trial will comply with the Data Protection Act, which requires data to be anonymised as soon as it is practical to do so.

#### **16.7. Expenses and Benefits**

Reasonable travel expenses for any visits additional to normal care will be reimbursed on production of receipts, or a mileage allowance provided as appropriate.

#### **16.8. Other Ethical Considerations**

No other ethical declarations to declare in relation to this study.

